7.7.2.2 Major Complications of CDI events

Major complications of CDI events include death, septic shock, toxic megacolon, colonic perforation, emergency colectomy, or ICU admission collected through the 6-month telephone assessment. Incidence of major complications of CDI events will be summarized by treatment arm after both the blinded and unblinded enemas.

7.7.2.3 Hospitalizations for Recurrent CDI

The number of subjects requiring hospitalization due to recurrent CDI through 8 weeks following the completion of the randomized study treatment will be summarized, along with the length of hospital stay, the number of subjects requiring ICU admission, and the length of ICU stay during hospitalization.

A listing of all hospitalizations due to CDI throughout the study will be generated.

7.7.2.4 Rate of onset of new chronic conditions comparing those treated with RBX2660 vs. Placebo.

Documentation of physician diagnosed chronic conditions for all subjects will be completed at baseline and compared to new physician diagnosed chronic conditions reported at 8 weeks, 3 months, and 6 months. Chronic condition is defined as a condition lasting >3 months. An initial assessment will be completed during the primary efficacy analysis as follow-up data allows with a complete analysis to be provided with the full study results. Additional analysis may be done of Placebo subjects who were documented treatment failures after blinded treatment then treatment successes following unblinded RBX2660 treatment.

8 STATISTICAL METHODS

8.1 General Methodology

All statistical tests will be two-sided with a significance level of $\alpha=0.05$, unless specified otherwise, and will be performed using SAS® Version 9.3 or higher. Confidence intervals (CI) will be constructed at the level of 95% unless specified otherwise. For continuous variables,

descriptive statistics (number of subjects [N], mean, standard deviation [SD], median, interquartile range [IQR], minimum, and maximum) will be generated. For discrete/categorical variables, the number and percentage of non-missing subjects will be generated. Descriptive statistics will be provided by treatment arm for all subjects. Standard operating procedures (SOPs) will be followed in the creation, validation and quality control of all data displays and analyses.

Subject listings of all data from the eCRFs as well as any derived variables will be presented.

8.2 Adjustments for Covariates

Adjustments for covariates will be made in sensitivity analyses of the primary endpoint if applicable due to imbalance of a particular covariate.

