4.4 Determination of Sample Size

To demonstrate a 69% success with one dose of the RBX2660 treatment group vs. 47% success in the Placebo control group, 240 subjects are required (power > 90%, nominal 2.5% type I error rate). Up to an additional 30 subjects will be enrolled to allow for a 10% loss-to-follow up rate, for a total of approximately 270 subjects. Considering the 2:1 randomization, this results in approximately 180 subjects in the RBX2660 arm and 90 subjects in the Placebo arm. Enrolled subjects who have signed consent and withdraw for any reason prior to administration of the first blinded enema will be replaced without counting toward the sample size cap. Replacement subjects will be randomized to ensure proper blinding.

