An analysis of time to CDI recurrence after completion of the assigned blinded treatment will be analyzed and presented by the Kaplan-Meier procedure and median duration presented by days (and weeks) using the ITT, mITT, and PP populations. The Kaplan-Meier estimate of the median time (days) and the associated 95% confidence interval will be presented for each treatment group. A graphic presentation of the Kaplan-Meier estimates will supplement the tabular presentation. Between group comparisons will be performed using the stratified log-rank test based on the stratification factor at randomization. The corresponding hazard ratio of the treatment effect along with the 95% confidence interval will be calculated using a Cox proportional hazard model with treatment and the stratification factor at randomization as explanatory variables.

Time to CDI recurrence is defined as the number of days from enema administration to first assessment indicating recurrence for those subjects who were deemed Treatment Failures with CDI recurrence. All subjects who are Indeterminate or discontinued for any reason prior to assessment of efficacy will be censored at the last assessment date at/prior to Week 8. For the analysis of Time to CDI recurrence within 8 weeks, all subjects considered as a treatment success will be censored at the date of their 8-week assessment. For the analysis of Time to CDI

recurrence through 6 months, all subjects considered to have achieved sustained clinical response will be censored at the date of their 6-month assessment.

Finally, the sensitivity of the primary efficacy endpoint will be assessed in a multivariate logistic regression adjusting for possible interactions of the following covariates with treatment group: age (< 65 years, \geq 65 years), sex (Female, Male), race group (White, Non-white), ethnicity (Hispanic-Latino, not Hispanic-Latino), site geography (outside the US, Eastern US*, Southern US*, Northern US*, Western US*), randomization strata (i.e., treatment received at the qualifying event) and number of previous episodes of CDI recurrence at baseline. Other baseline variables will be compared for balance using the appropriate statistical test. This analysis will be performed on all analysis populations where at least 20 subjects in each sub-group are available for analysis to fully understand the observed treatment effect.

*States included in the identified US geographical regions are as follows:

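### SAP 8.2 ties extra covariate adjustment to an undefined baseline imbalance; if the SAP's balance tests are the trigger, additional covariates are picked by chance rather than by prognostic value

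*SAP*

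**What the plan says.** SAP 8.2 consists of one sentence: "Adjustments for covariates will be made in sensitivity analyses of the primary endpoint if applicable due to imbalance of a particular covariate". It gives no measure of imbalance, no threshold and no list of covariates.

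SAP 7.6.1.2 has two elements that bear on this:

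- **A fixed model.** The sensitivity of the primary endpoint "will be assessed in a multivariate logistic regression adjusting for possible interactions of the following covariates with treatment group". The covariates are age group, sex, race group, ethnicity, site geography, randomization stratum and number of previous CDI episodes. There is no balance trigger, only a condition of at least 20 subjects per subgroup.
- **Balance tests for the rest.** "Other baseline variables will be compared for balance using the appropriate statistical test". The test is not named. SAP 8.1 makes all tests "two-sided with a significance level of $\alpha=0.05$, unless specified otherwise".

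The same section fixes a stratified log-rank test and a Cox model containing the stratification factor. Variables outside the seven are summarized at baseline under SAP 7.3. They include the Charlson index, the ATLAS score, and the duration, treatment and hospitalization of each earlier CDI episode. The primary analysis (SAP 7.6.1.1 and the Bayesian appendix) models responder counts by arm and study, without baseline covariates.

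**The concern.** Whether a covariate needs adjustment depends on how strongly it predicts recurrence, together with how far the arms differ on it. A balance test looks only at the second. In a properly randomized trial its null hypothesis is true by design, so each test flags 5% of covariates whatever their prognostic value.

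Read together, 8.2 and 7.6.1.2 therefore suggest a data-dependent rule. A strongly prognostic factor with a moderate imbalance would go unadjusted, while an irrelevant factor that happened to reach p < 0.05 would be adjusted for. If the balance test is not the intended trigger, 8.2 has no operational criterion, and the choice falls to judgement once data by arm are seen.

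At stake is the credibility of the adjusted sensitivity analyses. Because the primary model has no covariates, these analyses are the main check on whether chance imbalance explains part of the observed effect.

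**Working it through.** **Inputs.** SAP 4.4 gives the arm sizes: "Considering the 2:1 randomization, this results in approximately 180 subjects in the RBX2660 arm and 90 subjects in the Placebo arm". It also gives 240 evaluable subjects, or 160 versus 80 at 2:1. The test level is two-sided 0.05 (SAP 8.1). The documents do not give covariate prevalence, prognostic strength or the number of covariates tested. These are assumed below, with ranges.

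**Step 1: reproduce the plan's figure.** The SAP states: "To demonstrate a 69% success with one dose of the RBX2660 treatment group vs. 47% success in the Placebo control group, 240 subjects are required", with "power > 90%, nominal 2.5% type I error rate". With p_C = 0.47, p_T = 0.69 and pooled rate (0.47 + 2 × 0.69)/3 = 0.617:

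n_C = [1.96 × √(0.617 × 0.383 × 1.5) + 1.2816 × √(0.47 × 0.53 + 0.69 × 0.31/2)]² / 0.22² = (1.167 + 0.765)² / 0.0484 = 77.1, so 78 placebo and 234 in total.

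Power at 160/80 is 91.0%. The plan's figure reproduces, so these arm sizes are a sound basis for the rest.

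**Step 2: smallest observed imbalance that is flagged.** For a binary covariate with overall prevalence p:

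SE = √[p(1−p)(1/n_T + 1/n_C)], and the difference is flagged if it exceeds 1.96 × SE.

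At p = 0.5 and 160/80, SE = √[0.25 × (1/160 + 1/80)] = 0.0685 and the threshold is 13.4 points. At 180/90, SE = √[0.25 × (1/180 + 1/90)] = 0.0645 and the threshold is 12.7 points.

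| Overall prevalence | Threshold, 160/80 | Threshold, 180/90 | p for an observed 10 points (160/80; 180/90) |
|---|---|---|---|
| 50% | 13.4 points | 12.7 points | 0.14; 0.12 |
| 30% | 12.3 points | 11.6 points | 0.11; 0.09 |
| 20% | 10.7 points | 10.1 points | 0.07; 0.05 (0.053) |
| 10% | 8.1 points | 7.6 points | 0.015; 0.010 |

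The outcome is fixed by the observed difference. At 50% prevalence an observed 10-point imbalance is never flagged. An observed 15-point imbalance always is: z = 0.15/0.0685 = 2.19, p = 0.028, or z = 0.15/0.0645 = 2.32, p = 0.020. At 10% prevalence an observed 10-point imbalance is always flagged.

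Under randomization a 50% covariate differs by 10 points or more, in either direction, in 14.4% of trials at 160/80. It is flagged in 5%. So in about 14.4 − 5 = 9.4% of trials it differs by 10 to 13.4 points and goes unflagged.

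**Step 3: covariates flagged by chance.** With k independent covariates, P(at least one flag) = 1 − 0.95^k. This is 23% for k = 5, 40% for k = 10 and 64% for k = 20.

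**Step 4: what an unflagged imbalance can do.** The shift in the unadjusted difference is the imbalance times the difference in success rate between covariate levels. With a 10-point imbalance favouring RBX2660, 180/90, no treatment effect and success near 50% (SE 0.0645), the conditional one-sided error of an unadjusted test at 2.5% is 1 − Φ(1.96 − shift/0.0645):

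| Assumed prognostic difference | Shift | Conditional error |
|---|---|---|
| 10 points | 1 point | 3.6% |
| 20 points | 2 points | 4.9% |
| 30 points | 3 points | 6.7% |

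Simulation of 400,000 null trials agrees (160/80, 50% covariate, 55% overall success). An 8 to 12 point imbalance favouring RBX2660 with a non-significant balance test occurs in 9% of trials. In those trials, at an assumed odds ratio of 3, the unadjusted error is about 5% (4.8 to 5.1% across runs) and the Mantel-Haenszel adjusted error is 2.4 to 2.7%. At an odds ratio of 2 the figures are about 4% (3.9 to 4.2%) and 2.4%. Averaged over all trials the unadjusted error remains 2.5%.

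**The case against.** The strongest reply is that much of the protection is already planned. Seven covariates, including randomization stratum, age group and number of previous episodes, enter a logistic model whatever the balance, and the Cox model carries the stratification factor. On this reading 8.2, with its words on applicability, merely adds further covariates where they are imbalanced. That stands in part: the two sections sit poorly together but do not strictly contradict each other. It does not remove the gap. The logistic model is framed around interactions with treatment, specifies no main-effects adjusted treatment estimate and omits the Charlson index and ATLAS score.

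A reader might also be tempted by stronger claims, which the documents do not support:

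- *A non-significant test is taken as proof of balance.* The SAP says this nowhere. Section 8.2 names no test, and the link to 7.6.1.2 and 8.1 is an inference.
- *The tests miss about two thirds of 10-point imbalances.* The figures behind this (69% at 160/80, 66% at 180/90) are one minus the power against a true population difference, which randomization rules out. They also need prevalence near 50%. The relevant quantity is the observed imbalance, as in Step 2.
- *Adjustment covariates in general are chosen by chance.* This can apply only to variables beyond the seven.
- *The trial's error rate or primary decision is compromised.* The primary model has no covariates, so the trigger cannot change it. The conditional error rates in Step 4 describe an unadjusted test in a selected minority of trials.

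**Conclusion.** The point holds in limited form. Section 8.2 makes adjustment depend on an undefined imbalance. If the 7.6.1.2 test is the trigger, additional covariates such as the Charlson index or ATLAS score are selected by chance. At about 50% prevalence, observed imbalances below roughly 13 points are never flagged; the threshold falls to about 8 points at 10% prevalence. With 10 independent covariates, an assumed number, a chance flag occurs in 40% of trials. The practical effect in Step 4 rests on assumed prognostic strength. The consequence is confined to sensitivity analyses, and the primary Bayesian conclusion is unaffected. The point is still worth acting on, because a better method is available from data already collected.

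**What to change.** 1. In SAP 8.2, delete the imbalance trigger.
2. In SAP 7.6.1.2, delete the balance tests and report baseline differences descriptively.
3. Before unblinding, prespecify one adjusted sensitivity analysis of the primary endpoint, run whatever the observed balance: a logistic model with treatment and main effects for randomization stratum, age group and number of previous CDI episodes, plus the Charlson index if it is judged prognostic. Name the adjusted treatment estimate to be reported.
4. Keep the interaction model in 7.6.1.2 as a separate subgroup exploration.

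The cost is a few sentences, since the variables are already collected. There is a small downside if ATLAS is added. It already scores age, so the SAP must avoid counting age twice. Its inputs may also be missing at the qualifying episode: SAP 7.6.3.5 allows baseline values to be substituted, while SAP 8.3 rules out imputation. The SAP must therefore say how missing components are handled, or subjects may drop out of the adjusted analysis.

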8.3 Handling of Dropouts or Missing Data

No imputations will be used in analyses/summaries. However, a last observation carried forward analysis will be used for evaluation of the Cdif 32 scores. Missing safety data will not be imputed beyond the adjustments for adverse event data mentioned in Section 6.5.2.

8.4 Medical Monitor Adjudication

The Medical Monitor reviews and adjudicates all serious adverse events and other adverse events of interest to provide an objective, qualified judgment of the events. Adverse event review and adjudication includes the event description, onset date in relation to the treatment date, and the investigator's determination of causal relatedness to IP, the enema procedure, and pre-existing condition, as well as rating the event's severity and seriousness. The Medical Monitor will remain blinded throughout the study. However, the DSMB will be unblinded as needed to adjudicate specific adverse events as per the study stopping rules (see Section 8.5.1, below).

8.5 Efficacy Analyses and Data Monitoring

The EAC will adjudicate individual efficacy data at the time of the interim and final analyses. Interim analyses evaluating the primary efficacy endpoint are planned once 160 subjects (minimum) and 220 subjects in the mITT population have completed (i.e., completed the 8 week follow-up assessment and/or completion of the Treatment Outcome form). At each interim analysis, the study may declare early success, in which case enrollment is stopped and the sponsor will file for immediate approval. The study may also declare futility, resulting in the cessation of enrollment and follow-up.

A primary efficacy and safety analysis will be performed when 100% of subjects reach their 8-week assessment following blinded treatment or are documented treatment failures by the site investigator. Safety analysis will be completed for safety endpoints defined at or prior to 8 weeks following blinded treatment. Full safety results as well as unblinded RBX2660 efficacy data will be reported after all available subjects complete their last 6-month telephone assessment following their last study enema (blinded or unblinded).

To decrease the chance of introducing bias, the primary efficacy analyses will use efficacy data as reviewed and confirmed by the EAC. The study sites, subjects, and the medical monitor will remain blinded to the specific results and to individual randomized treatment assignments until the study is completed.

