A final analysis and report will be completed once the last subject has completed the 6-month follow-up visit for their study treatment. This includes 6-month follow-up after an unblinded RBX2660 study treatment. At that time the study will be considered complete.

See Figure 3-1 for an illustration of the Study Design.

[figure not shown]

Figure 3-1: Phase 3 Study Design. 2:1 randomization refers to two subjects randomized to receive RBX2660 (Group B) for every one subject randomized to Placebo (Group A)

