6.14. Unblinded RBX2660

Subjects with a documented treatment failure meeting the protocol definition in the blinded portion of the study may be scheduled for administration of an unblinded RBX2660 enema. In order to receive the unblinded RBX2660 enema, a subject must have documentation of the following:

- Meeting all treatment failure criteria as defined by the protocol
- Compliance to the washout period (discontinuation of antibiotics for 24-72 hours prior to administration visit) is confirmed
- Negative urine-dipstick pregnancy test for subject of childbearing potential to confirm that they are not pregnant on the date of administration
- Unblinded enema administration is to occur within 21 calendar days of failure determination

While subjects may choose to receive and understand they are receiving an unblinded RBX2660 enema; neither they nor the study site will be unblinded to their original treatment.

If antibiotics are given to control symptoms, a 24-72hr washout period prior to administration of an unblinded RBX2660 enema is required, however the unblinded enema must still be administered within 21 calendar days of failure determination.

If a subject receives an unblinded RBX2660 enema, the follow-up requirements will restart from the day of administration of the unblinded RBX2660 enema according to the same schedule as required for the blinded portion of the study. This results in completion of a new subject diary from the day of unblinded RBX2660 enema administration until the day prior to the 1-week visit; in-office visits at 1-week (see Section 6.8), 4- week (see Section 6.9) and 8-week (see Section 6.10) as well as telephone calls at 2, 3 and 6 weeks (see Section 6.11) and at 3 and 6 months (see Section 6.12) after the unblinded RBX2660 treatment.

The study will be considered complete when all subjects have reached their 6-month follow-up after the last study enema received, including unblinded enemas, or have exited, whichever is earlier.

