6.16. Subject Withdrawal or Termination

A subject's study participation is considered complete once the 6-month telephone call is conducted after starting the last course of study drug or the subject exits the study, whichever comes first. A subject may withdraw at any time for any reason or be withdrawn from the study prematurely for the following reasons:

- Withdrawal of consent by subject
- Lost to follow-up
- Failure to comply to study requirements
- Termination of study by the sponsor
- Death
- Other (to be specified).

The reason for withdrawal is recorded on the Study Exit eCRF. In the event that a subject requests to withdraw from the study, every attempt should be made to have the subject return for an early withdrawal visit and to complete the required visit questionnaires prior to withdrawal.

For a subject who is suspected of being lost-to-follow-up, a minimum of three attempts must be made to contact subjects using two different contact methods (e.g., telephone, email, text, and letter); one attempt must be a registered postal letter or traceable courier notice (e.g., FedEx Express) to the subject's last known address. The contact attempts and methods are to be recorded on the Study Exit eCRF. The date the subject is regarded as lost to follow-up is the date of last actual encounter with the subject, such as the last phone call contact or visit.

Completion of a Study Exit eCRF is required for all randomized subjects when they exit the study regardless of reason, including completion of all study requirements, visits and assessments. Subjects who were randomized but were determined to be screen failures or otherwise exited prior to receiving a dose of the study drug should also be documented on a Study Exit eCRF.

7. Assessment of Safety

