7.6.1. Initial Reports

All SAEs occurring from the time of informed consent until 6 months after administration of the last study enema of IP must be reported to Medpace Clinical Safety **within 24 hours** of the knowledge of the occurrence (this refers to any adverse event that meets any of the aforementioned serious criteria). All serious adverse events that the investigator considers related to study drug occurring after 6 months after administration of the last enema of IP must be reported to the Sponsor.

To report the SAE, complete the SAE form electronically in the electronic data capture (EDC) system for the study. When the form is completed, Medpace Safety personnel will be notified electronically and will retrieve the form. If the event meets serious criteria and it is not possible to access the EDC system, send an email to Medpace Safety at [contact] or call the Medpace SAE hotline (phone number listed below), and fax the completed paper SAE form to Medpace (fax number listed below) within 24 hours of awareness. When the EDC system becomes available, the SAE information must be entered within 24 hours of the system becoming available.

Safety Contact Information:
Medpace Clinical Safety

Medpace SAE hotline – USA:

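### SAP 8.5 ends follow-up on a futility stop, and this is not reconciled with the 6-month safety follow-up set elsewhere in the SAP and in the protocol

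*SAP*

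**What the plan says.** SAP 8.5 sets the timing of the interims: "Interim analyses evaluating the primary efficacy endpoint are planned once 160 subjects (minimum) and 220 subjects in the mITT population have completed". Early success at an interim ends enrollment, and nothing is said about follow-up. For futility the SAP goes further: "The study may also declare futility, resulting in the cessation of enrollment and follow-up". The safety stopping rule in SAP 8.5.1 only pauses enrollment. The futility section of the Bayesian appendix says the trial stops and does not mention follow-up. Futility is therefore the one outcome for which the SAP expressly ends follow-up.

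Other text points the other way:

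- SAP 8.5, next paragraph: full safety results are reported "after all available subjects complete their last 6-month telephone assessment following their last study enema (blinded or unblinded").
- Protocol 7.6.1: "All SAEs occurring from the time of informed consent until 6 months after administration of the last study enema of IP must be reported".
- Protocol 3.2: "A final analysis and report will be completed once the last subject has completed the 6-month follow-up visit for their study treatment".
- Protocol 6.14: "The study will be considered complete when all subjects have reached their 6-month follow-up after the last study enema received". That sentence goes on to cover unblinded enemas and to accept study exit where it comes earlier.

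The protocol also has a route to early ending. Section 6.16 lists "Termination of study by the sponsor" among the reasons for premature withdrawal, section 6.15 carries the same reason on the exit form, and section 3.2 leaves the details of the interim analyses to the SAP.

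**The concern.** A site or data manager holding both documents would not know what to do with treated subjects on the day futility is declared. The SAP ends their follow-up. The protocol's schedule and SAE window continue, and no text says that a futility decision counts as termination by the sponsor.

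The subjects affected are those treated most recently. RBX2660 contains live organisms (protocol 5.1), and donor-to-recipient transmission is on the list of anticipated events (protocol 7.3). Onset of new chronic conditions is a safety endpoint (protocol 2.6). SAP 7.7.2.4 defines chronic as lasting more than 3 months and compares baseline with 8 weeks, 3 months and 6 months. A subject cut off before month 3 cannot be shown within the study to have a new post-treatment condition that meets that definition.

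There is a smaller effect on the efficacy tables. Under SAP 6.3.1 a treated subject who exits before week 8 is a failure in the ITT analysis. Under SAP 6.3.2 the same subject is dropped from mITT if the exit is unrelated to CDI symptoms. Exits caused only by the futility decision would be scored one way in one table and removed from the other.

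**Working it through.** **Step 1. The passages side by side**

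| Place | End of follow-up | Condition |
|---|---|---|
| SAP 8.5, futility sentence | At the futility decision | Futility declared |
| SAP 8.5, next paragraph | Last 6-month call | All available subjects |
| Protocol 7.6.1 | SAE window to 6 months after last enema | None stated |
| Protocol 3.2 | Final report after last 6-month visit | None stated |
| Protocol 6.14 | 6-month follow-up | Or exit, if earlier |
| Protocol 6.16 | 6-month call | Or exit, including sponsor termination |

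The first row fits the last two only if a futility decision is treated as sponsor termination, which neither document says. It does not fit rows 2 to 4 unless those are read with an unwritten exception. In row 2, the word for available subjects could be stretched to exclude those whose follow-up was cut off, but the SAP does not say that it does.

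**Step 2. How often the rule would be used**

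Cumulative futility probabilities from the appendix, Table 4 (control rate 0.45):

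| True effect | By interim 1 | By interim 2 |
|---|---|---|
| 0 | 0.445 | 0.732 |
| +0.05 | 0.204 | 0.424 |
| +0.10 | 0.065 | 0.158 |
| +0.15 | 0.014 | 0.036 |
| +0.20 | 0.002 | 0.005 |

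The planned effect is 0.69 − 0.47 = 0.22, so under the planning assumption a futility stop is very unlikely. With no effect it is the most likely outcome. Across the other control rates tabulated, the no-effect figure by interim 2 runs from 0.555 (control 0.7) to 0.811 (control 0.3).

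The hierarchical model was not rerun. A crude simulation of interim 1 with no effect gave 0.545 with no borrowing and 0.34 with full pooling of the Phase 2b data. These bracket the SAP's 0.445 but do not reproduce it. The appendix also gives the futility threshold as 0.01 in Table 3 and 0.001 in the introduction to the example trials. Example Trial 2 stops at 0.003, which fits only 0.01. How often the stop triggers depends on which figure is used.

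**Step 3. How many subjects would be affected**

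The documents give no accrual rate. Let r be the number treated per week (assumed 1 to 5, steady), and take 6 months as 26 weeks.

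- No week-8 outcome yet: 8r
- Week 8 reached, month 6 not reached: (26 − 8)r = 18r
- All without the 6-month call: 8r + 18r = 26r
- On RBX2660 at 2:1 allocation: two thirds of each

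| r | No week 8 | Week 8 but no month 6 | Total | RBX2660, of total |
|---|---|---|---|---|
| 1 | 8 | 18 | 26 | 17 |
| 2 | 16 | 36 | 52 | 35 |
| 3 | 24 | 54 | 78 | 52 |
| 5 | 40 | 90 | 130 | 87 |

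The 270 maximum limits the first column to 270 − 160 = 110 at interim 1 and 270 − 220 = 50 at interim 2, ignoring the few treated subjects outside mITT. Neither cap binds in this range. Subjects whose clock restarts after an unblinded enema (protocol 3.8) are not counted and would add to the totals.

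**Step 4. What is not lost**

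At least 160 or 220 mITT subjects already have a week-8 outcome when the interim is run. All data up to the stop are kept. SAEs already under way are followed until they subside, stabilise or become chronic (protocol 7.6.2). Events causally related to the product or procedure are followed until they resolve or stabilise (protocol 7.8).

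**The case against.** A reader might infer that the protocol allows no exception and that the two documents cannot both be followed. The protocol does not support that. Section 6.14 accepts exit before 6 months, 6.15 and 6.16 name sponsor termination, and 3.2 hands interim details to the SAP. A futility stop carried out as a sponsor termination could satisfy most of the text.

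A reader might also infer that treated subjects in general would be left without safety or week-8 outcomes. That is wrong too. Only those still in follow-up lose anything, and those past week 8 lose only later assessments. Known SAEs and related events are still pursued, and section 7.6.1 asks for SAEs considered related even beyond 6 months. Once futility is declared, the outstanding week-8 outcomes serve no confirmatory test.

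All of this stands, and it limits the point. It does not remove it. Sections 6.15 and 6.16 permit early exit without saying that futility is such a case. The delegation in 3.2 concerns the interim analyses and does not say that the SAP overrides the SAE window. The duties in 7.6.2 and 7.8 cover events already known, whereas the scheduled visits and calls are what bring new ones to light. The conflict between adjacent paragraphs of SAP 8.5 does not depend on the protocol at all.

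**Conclusion.** The concern holds as an unreconciled conflict. SAP 8.5 attaches the end of follow-up to a futility decision and to no other outcome. The next paragraph of the same section and protocol 3.2 and 7.6.1 assume 6-month follow-up, and no passage says how treated subjects are handled after such a stop.

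If the sentence were applied, about 26 to 130 subjects would lose scheduled assessments, 8 to 40 of them before week 8. This rests on the assumed 1 to 5 treated per week and shows scale only. The event is likely if the product has little effect (73% with no effect, 42% at +0.05, control rate 0.45) and rare near the planned effect (0.5% at +0.20). The loss would therefore fall mainly in the setting where efficacy is in doubt and the safety record carries more of the weight. This should be fixed before the first interim. It does not threaten the validity of the primary test.

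**What to change.** Before the first interim:

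1. In the futility sentence of SAP 8.5, remove the reference to follow-up, so that futility ends enrollment, as early success does.
2. Add one sentence: subjects already treated complete their remaining scheduled week-8 and 6-month assessments, and these data are reported descriptively in the safety population.
3. Check the result against protocol 3.2, 6.14, 6.16 and 7.6.1, and say in the protocol whether a futility decision counts as termination by the sponsor under 6.16.
4. While the text is open, settle whether the futility threshold in the appendix is 0.01 or 0.001.

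The cost is a short SAP revision and, if futility is declared, completing the visits and calls that the protocol already schedules.
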